9.1.3 BASELINE DESCRIPTIVE STATISTICS

We will use SPSS Version 25¹⁸¹ to analyze descriptive statistics and generate histograms. These will be reviewed and visually inspected for potential nonnormality and outliers. If needed, appropriate data transformations will be applied, or alternative data procedures (e.g., nonparametric, bootstrapping) will be used. Special attention will be paid to the distribution of cannabis use to determine if alternate analytic strategies are needed if rates are low.¹⁸²

9.1.4 TABULATION OF INDIVIDUAL PARTICIPANT DATA

Individual participant data will be listed by measure and time point.

10 REGULATORY, ETHICAL, AND STUDY OVERSIGHT CONSIDERATIONS

10.1.1 INFORMED CONSENT PROCESS

10.1.1.1 CONSENT AND OTHER INFORMATIONAL DOCUMENTS PROVIDED TO PARTICIPANTS

Consent forms describing in detail the study intervention, study procedures, and risks are given to the participant and written documentation of informed consent is required prior to starting the intervention. The following materials are submitted with this protocol:

- Adult consent form
- HIPAA authorization form
- Participant discharge flyer outlining study schedule and contact information for the study.
Importantly, this flyer does *not* disclose anything about the assault.
- Planned email and text communications

10.1.1.2 CONSENT PROCEDURES AND DOCUMENTATION

Full study consent is obtained at the time of presentation for care. Each consent is obtained by traditional in-person consent or by electronic teleconsent (detailed below). A potential participant must provide consent to participate. The RA will explain the study and answer any questions from the potential participant, emphasizing the voluntary nature of the study and the ability for the participant to cease or withdraw their participation at any time. A signed copy of the consent form will be given to the participant. Consent will be obtained via REDCap, and it will be documented and timestamped in the study tracking database prior to the initial assessment.

Teleconsent is used as a consent option, because it has been widely shown to be a safe and valid method of obtaining consent in medical settings,^{189,190} and because it addresses barriers that prevent critically needed research in settings where it is very difficult to consistently physically provide trained research staff at the time and place necessary for consent. (In this study, and more generally in research, teleconsent also addresses inequities created by the fact that research staff are more difficult to hire/provide in socioeconomically disadvantaged and/or rural areas). Teleconsent facilitates the consent process and provides the same opportunity to make an informed and voluntary decision as a traditional consent. Importantly, the teleconsent platform used in this study complies with Health Insurance Portability and Accountability Act (HIPAA) requirements by (1) encrypting all transmitted data, (2) not storing patient information, (3) keeping an audit trail of the consent process, and (4) signing a business associate's agreement (BAA) with the user.

Teleconsent is obtained in the following manner. The SANE nurse approaches the potential participant at the time of her SANE exam to assess her willingness to speak to an RA about participation in an ongoing study via

laptop or tablet. If the potential participant is willing, an individual at the local site will notify the on-call teleconsent RA with an estimate for when the participant will be ready to speak. Alternatively, if patient requests, the SANE may schedule an appointment time in a secure communication platform, within 24 hours, to meet directly with the teleconsent team to complete informed consent and the remainder of the enrollment process.

Once ready, the SANE uses the study laptop or tablet to open Zoom and joins the teleconsent RA's HIPAA-enabled Zoom meeting room. If the patient chooses to meet with RA within 24 hours, the RA will send the patient a Zoom meeting invite and join the meeting room at the scheduled time. The RA introduces her/him/themself via live two-way video communication and describes her/his/their role as a research associate in an ongoing study testing an app-based intervention to aid recovery after sexual assault. Just as in person, if the potential participant is willing, the RA reviews the study consent and requirements for participation in real-time, and uses the online database to screen the potential participant for study eligibility. If eligible, the teleconsent RA opens DocuSign – a secure eConsent platform – and sends the consent, HIPAA authorization, and social security number collection forms to the participant's email inbox. Both the participant and the teleconsent RA will open and review the documents. Because both the RA and the participant will have the forms open, the participant can follow along on her screen while the RA explains each section. This allows teleconsent to be an interactive and engaging experience, similar to in-person consent, and facilitates a careful explanation and discussion of the consent document.

After reviewing the consent documents on the laptop or tablet, if the potential participant is willing to participate, the RA and participant both electronically sign the consent through DocuSign and enter their time of signature (the date of signature is automatically piped in by DocuSign). DocuSign only allows the participant and RA to sign and timestamp their respective sections (i.e. the RA cannot mistakenly sign on behalf of the participant, and vice-versa), protecting the integrity of the consent process.

Figure 6 Example of RA signature field.

This section is to be completed by the research team member who obtained consent:
I have explained this study and the procedures to the above participant in terms they could understand. They freely consented to take part in this study.

RA Name _____
Name of Person Obtaining Consent (PRINTED) _____

Signature of Person Obtaining Consent _____

12/11/2020 Date  Time 

When the consent document is complete, DocuSign checks to ensure all data fields have been filled out. If required fields have not been completed, the document automatically scrolls to display the first missing field. When the document is completely filled out, a PDF file of the completed consent, HIPAA, and SSN documents is generated and emailed to the participant, and the RA saves a copy to the central, secure online study database.

10.1.2 STUDY DISCONTINUATION AND CLOSURE

If participants in the active group exhibit, on average, clinically significant exacerbations in ASI scores (transition from scores <25 to ≥ 25), PCL-5 scores (12-point increase, scaled based on the 10-point cut-off used in PCL-IV¹⁹¹), or MPS scores (increase of 8 pts¹⁹²), then the investigative team will review the findings to evaluate the safety of continuing with the trial. This study may be temporarily suspended or prematurely terminated if there is sufficient reasonable cause. If the study is prematurely terminated or suspended, the Principal Investigator (PI) will

promptly inform the Institutional Review Board (IRB) and will provide the reason(s) for the termination or suspension. Study participants will be contacted, as applicable, and be informed of changes to the study activity schedule.

Circumstances that may warrant termination or suspension include, but are not limited to:

- Determination of unexpected, substantial, or unacceptable risk to participants
- Insufficient compliance to protocol requirements
- Data that are not sufficiently complete and/or evaluable
- Determination that the primary endpoint has been met
- Determination of futility

Study may resume once concerns about safety, protocol compliance, and data quality are addressed, and satisfy the IRB.

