6 STUDY DESIGN

6.1 OVERALL DESIGN

6.1.1 PARTICIPANTS

Women (natal and self-identifying) presenting for emergency care within 72 hours of sexual assault to one of our sites (Section 6.8.1) and who meet eligibility criteria (Sections 6.5 and 6.6). As we are interested in incident substance use post-assault, women will not be required to be cannabis or other substance users at the time of assault. However, our pilot data suggest >50% of sexual assault survivors with high AS use cannabis, thus we expect our final sample will include high rates of CUD without this inclusion criterion.

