6.1.8.2 RELAXATION CONTROL

Breathe2Relax¹⁵⁶ is a mobile application that instructs users on diaphragmatic breathing, a coping tool in which slow breathing through the diaphragm reduces anxiety.^{157,158} Participants in the control condition will download Breathe2Relax to their smartphones and receive SMS reminders to engage with the app. The control intervention is expected to reduce symptoms, but not as much as the CBT strategies taught in RISE Guide.^{159,160}

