7.2 EFFORTS TO MINIMIZE BIAS

Randomization tables will be generated by the study Biostatistician and uploaded into the study REDCap database by the UNC Research Coordinator prior to launching data collection. Participants are randomized (1:1) to receive either the RISE Guide (experimental) condition or Breathe2Relax (control) condition after completing their 1-week survey. The list of assignments will be stored securely in REDCap.

Participants will *not* be masked to their study conditions, as branding is visible in both RISE Guide and Breathe2Relax. Moreover, the UNC Research Coordinator will not be masked to condition, as they will be responsible for tracking RISE Guide progress and managing participant payments. The Principal Investigator, Biostatistician, Site Principal Investigators, Site Research Associates, and anyone involved in data analysis will remain masked to condition until data analysis is complete; masking will be maintained through reduced data viewing privileges in REDCap.

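### The safety-review prompt in section 10.1.2 rests on active-arm averages with no control comparison, and its review step is not reconciled with the masking in section 7.2

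*Combined protocol and SAP*

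**What the plan says.** Section 10.1.2 opens with the condition "If participants in the active group exhibit, on average, clinically significant exacerbations in ASI scores". For the ASI this is a "transition from scores <25 to" 25 or above. For the PCL-5 it is a "12-point increase, scaled based on the 10-point cut-off used in PCL-IV". The third criterion reads "or MPS scores (increase of 8 pts". If one is met, "then the investigative team will review the findings to evaluate the safety of continuing with the trial". The section mentions no control arm, reference visit or look schedule, and does not say who calculates the averages.

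Four other places bear on this:

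- **Expected course.** Section 6.1.8.2 states: "The control intervention is expected to reduce symptoms, but not as much as the CBT strategies taught in RISE Guide". Section 6.1.5 adds that ASI scores may fall in the control group as well, and declines to give a size for the change.
- **Cannabis use.** Section 6.1.1 does not require use at entry, because new use after the assault is of interest. It reports that "our pilot data suggest >50% of sexual assault survivors with high AS use cannabis".
- **Masking.** Section 7.2 masks the Principal Investigator, the Biostatistician, site investigators and site research associates, and says that "anyone involved in data analysis will remain masked to condition until data analysis is complete". The UNC Research Coordinator is unmasked.
- **Other safety data.** Section 8.2.4 records an adverse event when a woman's anxiety, depression or PTS score doubles and passes a cutoff. Section 8.2.5 sends serious events, and events that are unexpected or possibly related, to the IRB within 7 days. Section 9.1.2 counts adverse events by condition, without saying when. Section 10.1.2 itself gives an open list of grounds for suspension.

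**The concern.** A rise in the active-arm mean measures change over time. It does not measure the effect of RISE Guide. Where recovery is expected in both arms, an intervention that slows recovery can leave women well behind control while their own average stays flat or falls. Where both arms worsen for outside reasons, the same prompt can be met although the intervention does nothing. The randomized control arm separates these two cases, and its data are already collected, but the prompt does not use it.

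The MPS criterion has a further difficulty. Women who do not use cannabis throughout are averaged in with those who do.

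There is also a procedural conflict. The prompt needs active-arm results during the trial, and the team that reviews them includes people whom section 7.2 keeps masked until analysis is complete.

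At stake is whether a group of recently assaulted women doing worse on the new intervention would be noticed through the one mechanism that looks at arm-level symptom scores.

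**Working it through.** The plan gives no false-alarm rate, power or look schedule for this prompt, so there is no stated figure to reproduce. What follows is an illustration.

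**Inputs from the documents.** PCL-5 trigger 12 points and MPS trigger 8 points (10.1.2). Enrolment 150 with 37 expected lost or incomplete (2.1), and 1:1 allocation (9.1). This leaves 150 − 37 = 113 women, or about 56 per arm. The share of cannabis users is above 50% (6.1.1).

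**Assumptions, not in the documents.** Fall in control-arm PCL-5: r = 0 to 15 points. SD of PCL-5 change: 18, with a range of 12 to 24. MPS change of zero in women who remain non-users. A single look with all 56 women per arm. I use the PCL-5 because the ASI criterion is a crossing of 25, which depends on a baseline mean that the plan does not give.

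**Step 1: harm needed to reach the trigger.** If RISE Guide is h points worse than control, the active mean change is h − r. Setting h − r = 12 gives h = 12 + r.

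**Step 2: probability that the prompt is met at h = 12.** P = 1 − Φ[(12 − (h − r)) / (SD/√n)]. With SD 18 and n = 56, the standard error is 18/√56 = 2.41.

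| r | Relative harm needed | Active mean change if h = 12 | P(prompt met) |
|---|---|---|---|
| 0 | 12 | +12 | 0.50 |
| 5 | 17 | +7 | 0.02 |
| 10 | 22 | +2 | <0.001 |
| 15 | 27 | −3 | <0.001 |

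At r = 10 the probability stays below 0.001 for SD 12 to 24. If the true relative harm is 18 points at r = 10, the active mean change is +8 and the probability is 0.006, 0.05 and 0.11 for SD 12, 18 and 24.

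**Step 3: the same harm seen against control.** The standard error of the difference is 18 × √(2/56) = 3.40. For h = 12, a two-sided 5% comparison has power Φ(12/3.40 − 1.96) = Φ(1.57) = 0.94. It is 1.00 at SD 12 and 0.75 at SD 24. None of these depends on r.

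**Step 4: the opposite error.** If both arms worsen by 12 points and there is no relative harm, the active mean change is 12 and the prompt is met with probability 0.50.

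**Step 5: MPS dilution.** If women who remain non-users stay at zero, the mean rise needed among users is 8 ÷ (share of users): 8/0.50 = 16, 8/0.60 = 13.3, 8/0.75 = 10.7, 8/1.00 = 8. This applies to the MPS only.

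**Step 6: masking.** Section 10.1.2 has the investigative team review active-arm findings while the trial runs. Section 7.2 keeps the Principal Investigator, Biostatistician and all analysts masked until analysis is complete. The coordinator could compute the averages, but no text assigns that task or says how the review proceeds without revealing arm-level results to masked staff.

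**The case against.** The strongest reply is that this prompt is not the trial's only protection and is not a stopping rule. It calls for a review. Individual symptom doubling is recorded woman by woman, so improvement in others cannot cancel it. Section 8.2.5 adds prompt IRB reporting. Section 4.1.1.1 has the lead coordinator review self-report data every two weeks so that the Principal Investigator can call women who appear at high risk. Section 10.1.2 allows suspension on other grounds. All of this stands, so a reader should not infer that relative harm would be hidden from the whole trial. What remains is that none of these routes is tied to the prompt and the adverse-event counts by condition have no timing. The doubling rule has no ASI or MPS criterion, and it can miss a change that 10.1.2 treats as clinically significant: a woman at PCL-5 35 who rises 12 points reaches 47, not the 70 that doubling requires.

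A reader might also infer that the prompt cannot be run because staff are masked. The documents do not support that, because the Research Coordinator is unmasked. The supported point is the missing assignment and the conflict over who reviews.

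Nor do the documents support saying that women who were not using cannabis at entry cannot register on the MPS. They may start, and section 6.1.1 admits them for that reason. Only those who remain non-users dilute the average.

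Finally, the probabilities rest on assumed values. Since no reference visit is named, the natural course from that visit is not fixed either. That is a fair limit on the size of the problem, but not on its direction where the control arm improves.

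**Conclusion.** The point holds in limited form. The prompt in 10.1.2 compares the active arm only with its own past. Given the recovery that the protocol expects, the active arm must be 12 + r PCL-5 points worse than control before its mean reaches the trigger. That relation is arithmetic; r itself is an assumption. At r = 10, SD 18 and 56 women per arm, a relative harm equal to the plan's own 12-point threshold would almost never meet the prompt (probability below 0.001), whereas a between-arm comparison would have power of 0.94 (0.75 to 1.00 over SD 24 to 12). At r = 0 recovery hides nothing.

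The MPS dilution is real but conditional. It is largest at 50% users, the floor of the protocol's expectation, and smaller above it.

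Sections 10.1.2 and 7.2 conflict on review during masking and must be reconciled. None of this shows that the thresholds are wrong or that the trial lacks other safety monitoring. The change is worth making because it is cheap and uses data already in hand.

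**What to change.** Leave the thresholds and the review decision with the clinicians. Add to section 10.1.2 that the unmasked Research Coordinator prepares the same summary for both arms under coded labels, at stated times and from a stated reference visit. The reference visit matters: by section 6.1.5 the ASI-3 is taken both in the ED and at 1 week, and randomization follows the 1-week survey. The summary would show:

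- mean change per arm on ASI-3, PCL-5 and MPS;
- the between-arm difference with its confidence interval;
- the number of women in each arm meeting each existing threshold;
- MPS also among women reporting any cannabis use up to that assessment, so that new users are kept.

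The counts need both arms. With no mean change and SD 18, chance variation alone would put 1 − Φ(12/18) = 25% of women at a rise of 12 or more.

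State that the table informs the reviewers and creates no new trigger. Reconcile sections 10.1.2 and 7.2 on who computes arm-level results and who sees them.

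The cost is a small recurring table from existing data. The downside is that reviewers see safety data by coded arm while the trial is running.

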Self-report. The ASI-3⁵² will be completed at ED visit, 1 and 7 weeks, and 6 months to measure AS. We expect that individuals will go from above the clinical cut-off of the ASI (17) to below. There is no specific expected magnitude in AS change, as this will depend on individuals' initial levels of AS. It is expected that those in the control group may also have reductions in ASI, but to a lesser degree than those in the active group. The Marijuana Problems Scale (MPS) measures problems related to cannabis use (CUD symptoms). The Marijuana Motives Measure (MMM) includes a coping subscale to be used as an outcome measure. This measures using cannabis to cope with distress, which is a risk factor for CUD. The CIDI-SC measures the quantity/frequency of cannabis use regardless of whether or not this use is problematic, and is also a secondary outcome measure. Finally, the Marijuana Cravings Questionnaire (MCQ) measures state cravings to use cannabis. The total and emotionality subdomains (measuring cravings to use cannabis to cope with emotions) will be used as secondary outcomes.

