6.1.6 SELF-REPORT ASSESSMENTS

Clinical assessments (Table 2) will occur remotely via REDCap, a reliable and valid method of data collection.¹³⁷ Treatment acceptability will be measured at 1 week via the Credibility/Expectance Questionnaire (CEQ),¹⁴⁵ Treatment Acceptability/ Adherence Scale (TAAS),¹⁴⁶ and 7 weeks with a study-specific measure with open-ended questions. PTS, CUD and secondary outcomes will be assessed at 6 months, allowing for temporal mediation tests. Demographic information will be collected on the one-week survey. Current medication use will be collected at one and seven weeks, and six months.

Table 2. Select Measures by Domain and Time Point

Domain	Measure	ED	EMA	1-wk	7-wk	6-mo	12-mo*
Anxiety	Patient-Reported Outcomes Measurement Information System (PROMIS) - Short Form 8a ¹⁴⁷			X	X	X	
Pre-SA Anxiety	Patient-Reported Outcomes Measurement Information System (PROMIS) - Short Form 8a ¹⁴⁷ , Retrospective				X		
Anxiety sensitivity	Anxiety Sensitivity Index-3 (ASI-3) ⁵²	X		X	X	X	
Depression	PROMIS - Short Form 8b ¹⁴⁷			X	X	X	
Pre-SA Depression	PROMIS - Short Form 8b ¹⁴⁷ , Retrospective			X			
Posttraumatic Stress	PTSD Checklist (PCL-5) ¹⁴⁸ , adapted for assault as index trauma and Ecological Momentary Assessment (EMA) when relevant	X	X	X	X	X	
Stress Reactivity	Empatica E4 (6 weeks post-assault), Positive and Negative Affect Schedule (PANAS) ¹³⁸	X	X				
Substance Use	Composite International Diagnostic Interview Screening Scales (CIDI-SC), daily use and quantity ¹⁴⁹	X	X	X	X	X	
Problematic Cannabis & Substance Use	Cannabis : Marijuana Problems Scale (MPS), ¹⁵⁰ Marijuana Motives Measure (MMM), ¹⁵¹ Marijuana Craving Questionnaire (MCQ) ¹³⁹ ; Other : Alcohol Use Disorder Identification Test (AUDIT) ¹⁵² , Drug Abuse Screening Test (DAST), ¹⁵³ Fagerstrom Test for Nicotine Dependence (FTND) ¹⁵⁴			X	X	X	X
Treatment Credibility / Acceptability	Credibility/Expectancy Questionnaire (CEQ), ¹⁴⁵ Treatment Acceptability/Adherence Scale (TAAS), ¹⁴⁶ study specific measure of usability			X	X		

* Self-report assessments and contact information updates are only conducted at the 12-month (365-393 day) timepoint for participants who consented to this study prior to the timepoint's removal in version 2.4 of this protocol.

6.1.7 3.5 MONTH CONTACT UPDATE

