6.5 INCLUSION CRITERIA

In order to be eligible to participate in this study, an individual must meet all of the following criteria:

- Provision of signed and dated informed consent form
- Stated willingness to comply with all study procedures and availability for the duration of the study
- Women sexual assault survivors presenting for emergency care \leq 72 hours post-assault at one of our study sites
- Able to speak, read, and write English
- 18+ years of age
- Able to provide informed consent
- Have a smartphone with continuous service \geq 1 year
- Reports elevated AS (>17 on the ASI-3)

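### The ASI safety-review trigger in Section 10.1.2 is a crossing of 25, so it cannot register worsening in an active arm whose mean is already 25 or more

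*Combined protocol and SAP*

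**What the plan says.** Section 10.1.2 sets three quantitative triggers, applied to active-arm participants. They are to be met if those participants "exhibit, on average, clinically significant exacerbations in ASI scores (transition from scores <25 to" 25 or more, or show a worsening in "PCL-5 scores (12-point increase" or in "MPS scores (increase of 8 pts". If one is met, "then the investigative team will review the findings to evaluate the safety of continuing with the trial". The section does not name the assessment from which change is counted, does not say how the average is formed, and gives no source for the value 25.

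The entry criterion in Section 6.5 is "Reports elevated AS (>17 on the ASI-3", and neither 6.5 nor 6.6 sets an upper limit. Section 6.1.5 places the ASI-3 at the ED visit, 1 week, 7 weeks and 6 months. Table 2 in Section 6.1.6 also has the PCL-5 and the MPS at 1 week. Section 7.2 places randomisation after the 1-week survey.

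**The concern.** A harm trigger should respond to harm wherever the group starts. The PCL-5 and MPS triggers do this because they measure change. The ASI trigger measures whether a line has been crossed, and a group already past the line cannot cross it again. The trial selects women for high anxiety sensitivity, so the starting point may well lie near or beyond 25.

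Anxiety sensitivity is also what RISE Guide is designed to act on. If the intervention raised it, this trigger is the stated rule that should notice. Under one plausible set of starting values it would stay silent however large the rise.

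**Working it through.** The plan states no figure to reproduce; the check is on the logic of the rule.

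**1. The rule as written.** It is met when reference score < 25 and later score ≥ 25. Minimum rise needed = 25 − reference score, defined only when the reference is below 25.

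| Reference ASI-3 | Rise needed |
|---|---|
| 18 (lowest eligible whole score) | 25 − 18 = 7 |
| 20 | 25 − 20 = 5 |
| 22 | 25 − 22 = 3 |
| 25 or more | no rise suffices |

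A move from 25 to 37 (+12) or from 30 to 50 (+20) does not meet the rule. A PCL-5 rise of 12 meets its own trigger from any starting level at which the scale has room.

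**2. Both readings of the averaging.** Read as an arm mean, a move from 25.0 to 35.0 is not a crossing. Read person by person, a woman who starts at 25 or more can never count as a crossing. The gap is present either way.

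**3. Can the reference be 25 or more?** Eligibility allows it. How likely it is cannot be derived, because the documents give no ASI mean, SD or ED-to-1-week correlation. As assumptions only:

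- ED-visit mean, taken as the mean of a normal distribution cut off below 17.5. A source mean of 10–25 with SD 8–15 gives 21.8 to 32.6. A source mean of 20–40 with SD 8–16 gives 24.9 to 42.6.
- 1-week mean = source mean + r × (ED mean − source mean), for the first set. Lowest: 10 + 0.6 × (21.8 − 10) = 17.1. Highest: 25 + 0.8 × (32.6 − 25) = 31.1.

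These ranges lie on both sides of 25. They show that the blind region is reachable, not how often it would be reached.

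**4. Is ASI covered elsewhere?** The symptom-worsening rules in Section 8.2.4 cover PROMIS anxiety, PROMIS depression and the PCL-5. The two-weekly data review in Section 4.1.1.1 looks for individual women at high risk. The general grounds for suspension in Section 10.1.2 carry no ASI criterion. No second quantitative ASI harm rule was found.

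**5. Which reference assessment?** Table 2 lists the MPS from 1 week onward, not at the ED visit. The 1-week survey is therefore the pre-randomisation assessment that all three scales share.

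**6. What the interim rule in the fix would require.** A mean increase has a 95% interval above zero when it exceeds about 1.96 × s/√n, where s is the SD of change. Assume s = 8 to 12, with n = 75 (150/2) or 56 ((150 − 37)/2, rounded down):

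- smallest: 1.96 × 8/√75 = 1.8 points
- largest: 1.96 × 12/√56 = 3.1 points

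With fewer women at an early review, the required increase is larger. With no true change, such a rule is met in about 2.5% of single looks.

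**The case against.** The strongest reply is that little depends on this trigger. It opens a discretionary review. The PCL-5 and MPS triggers, the individual worsening rules in 8.2.4, the two-weekly review, 7-day IRB reporting (8.2.5) and the open-ended grounds for suspension all remain, and they cover symptoms that anxiety sensitivity is said to drive. This stands, and it limits the point to a minor one. It does not close the gap, since none of these tracks ASI itself.

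A second reply is that the protocol treats anxiety sensitivity by cut-off throughout. Section 6.1.5 frames benefit as moving below 17 and says "There is no specific expected magnitude in AS change, as this will depend on" initial levels. That passage concerns expected benefit and does not set the harm rule. If change depends on where a woman starts, a single fixed line is a weaker harm rule, not a stronger one.

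Two stronger readings are tempting, and the documents support neither. A reader might infer that the trigger will usually be unable to fire. Any such frequency comes from the assumed distribution and changes with it. A reader might also infer that the trigger is over-sensitive, because a very small rise from just under 25 would meet it. The wording allows that, but it needs a reference mean that happens to sit just below 25, which nothing in the documents indicates. The protocol also expects anxiety sensitivity to fall, since "those in the control group may also have reductions in ASI, but to a lesser degree than those in the active group", and a needless firing costs only a team review.

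**Conclusion.** The point holds as a gap in a stated rule. As written, the ASI trigger cannot register any worsening from a reference of 25 or more, under either reading of the averaging. The eligibility criteria permit such a reference, and no other quantitative rule covers ASI. This conclusion follows from the text and needs no assumed data.

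Its size is minor. The trigger leads to review rather than stopping, other safeguards remain, and the probability that the active arm sits at 25 or more cannot be derived from the documents. The ranges under working are illustrations and should not be read as evidence of size.

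**What to change.** In Section 10.1.2:

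- Keep the crossing of 25 and add an alternative ASI trigger that applies at any starting level: a mean active-arm increase in ASI-3 from the 1-week, pre-randomisation assessment of at least a prespecified number of points.
- Have the sponsor's clinicians set that number, with a rationale, before any further review of data by arm. The documents give no basis for a value.
- Until a value is justified, use a mean increase whose 95% confidence interval excludes zero. This is a statistical stopgap and not a clinical threshold.
- Name the 1-week assessment as the reference for the ASI, PCL-5 and MPS triggers.

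Naming the reference alone would not be enough, because an arm at 25 or more at 1 week would still be outside the ASI rule. Sections 6.1.5 and 6.5 need no change.

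The cost is a short amendment, which Section 2.2 requires the IRB to approve, and possibly a few more team reviews. No new data are needed, since all three scales are already collected at 1 week.
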